	Screening	Day-1	Pre-dose	0	0.5	0.75	1	1.5	2	4	6	8	10	12	24	48	
Serum FSH	X															Postmenopausal women only. See Appendix 2 and 5.	
HIV, hepatitis B and C screen	X															Per site SOP.	
Drug Screen	X	X														Drug screening is mandatory; any additional assessments are conducted per site SOP.	
Hematology/Chemistry	X	X														X	See Appendix 2
Urinalysis	X	X														X	See Appendix 2
AE/SAE review	X															X	See Section 8.4
Pharmacokinetics																	
Blood for Plasma MK-3402			X		X	X	X	X	X	X	X	X	X	X	X	See Section 8.6.1	
Urine for MK-3402			X	X													Collected: Predose (spot collection), 0-4 hrs, 4-8 hrs, 8-12 hrs and 12-24 hrs postdose. See Section 8.6.2
Biomarkers																	
Blood for Genetic Analysis			X														Collect Predose from enrolled participants only. See Section 8.8.

AE=adverse event; BMI=body mass index; BP=blood pressure; DNA=deoxyribonucleic acid; ECG=electrocardiogram; FBR=future biomedical research; FSH=follicle stimulating hormone; HIV=human immunodeficiency virus; HR=heart rate; ID=identification; IV=intravenous; RR=respiratory rate; SAE=serious adverse event; SOP=standard operating procedure; VS=vital signs.

### 1.3.3 Panel E Period 2

Study Period:	Pre-dose	Intervention (hours)														Post-study a	Notes	
		0	0.5	0.75	1	1.5	2	2.5	3	3.5	4	4.5	6	8	10	12	24	48
Administrative Procedures																		
Concomitant Medication Review		X-----														X-----		See Section 8.1.5
Study Procedures																		
MK-3402 IV Administration		X-----X																Infusion of 100-mL solution over ~30 minutes (start t=0).
Standard Meals													X-----X					See Section 5.3.1
Domiciling	X-----												X-----					See Section 8.1.11
Safety Procedures																		
Full physical examination	X															X	See Section 8.3.1	
Weight																X	BMI to be calculated only at screening.	
Vital Signs (HR, BP, RR, body temperature)	X	X				X						X		X		X	See Section 8.3.2	
12-lead ECG	X	X				X								X			See Section 8.3.3	
1-minute ECG rhythm strip		X															See Section 8.3.3.	
Hematology/Chemistry	X													X			See Appendix 2	
Urinalysis	X													X			See Appendix 2	
Hemodialysis			X														HD session will be initiated immediately following the 0.5-hr postdose blood draw, VS and ECG.	
AE/SAE review	X-----															X		

Panels E Period 2 (MK-3402 Administered Pre-Dialysis)																			

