## 3 HYPOTHESES, OBJECTIVES, AND ENDPOINTS

The study will be conducted in male and female (non-childbearing potential only) participants, 18 to 75 years of age with mild, moderate or severe renal impairment, end stage renal disease, or healthy adults.

Objectives	Endpoints
Primary	

• Objective: To compare the plasma PK (eg, AUC0-inf, Ce0i, Tmax, elimination terminal t1/2, CL, and Vd) of MK-3402 following a single IV dose in participants with varying degrees of renal impairment (mild, moderate, severe, ESRD before HD, ESRD after HD) to those of healthy matched control participants.

• Estimation: MK-3402 AUC0-inf following a single IV dose of MK-3402 administered to participants with varying degrees of renal impairment (mild, moderate, severe, ESRD before HD, ESRD after HD) will be estimated and compared to MK-3402 AUC0-inf when administered to healthy matched control participants.

Secondary	

• Objective: To investigate the extent MK-3402 is removed by hemodialysis.

• Estimation: The extent to which MK-3402 is removed by hemodialysis from the plasma (eg, CLD, plasma) or the dialysate (eg, CD, AED, AED (%dose), CLD, dialysate) will be estimated.

Objectives	Endpoints

Objective: To compare the urine PK (eg, Ae0-24, Fe, CLr) of MK-3402 following a single IV dose of MK-3402 to participants of varying degrees of renal impairment, where possible, to those of healthy matched control participants.

Estimation: MK-3402 Ae0-24, Fe, and CLr following a single IV dose of MK-3402 administered to participants with varying degrees of renal impairment, as appropriate, will be estimated and compared to those estimated in mean healthy matched control participants.

	

Urine MK-3402 Ae0-24, F3, and CLr

Objective: To evaluate the safety and tolerability of the administration of a single IV dose MK-3402 in participants with varying degrees of renal impairment.

	

Adverse events, vital signs, 12-lead electrocardiograms, laboratory safety tests

Tertiary/Exploratory	

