Enrollment in Panel D will commence following the completion of enrolment of Panels A and B. Six healthy control participant will be matched to the mean age ( $\pm$  15 years) and the mean BMI ( $\pm$  10%) of the participants in Panels A and B combined.

The data from the already enrolled healthy participants who satisfy the mean age and BMI matching criteria of the RI participants in Panels C and E will be used. However, if any of the healthy participants do not meet the matching criteria described above, additional healthy participants will be enrolled to result in a total of 12 healthy participants who match the mean

age ( $\pm$  15 years) and the mean BMI ( $\pm$  10%) of Panel C and E, to be assessed independently. The sex of the additional healthy participant(s) will be selected to ensure that there is a minimum of 2 participants of each sex in the group of participants within Panel D who match with Panels C and E.

The PK comparisons between each RI panel (Panels A, B, C, and E) and healthy controls will include only the control participants who meet the matching criteria for the respective RI panel.

In all Panels, MK-3402 will be administered IV over approximately 30 minutes.

Participants in Panels A, B, C, and D will receive a single IV dose of MK-3402. Plasma samples will be taken at prespecified time points up to 48 hours (Panels A, B, C and D) and urine samples will be taken at prespecified time points up to 24 hours postdose, where possible, for PK assessment of MK-3402.

Participants in Panel E will receive a single IV dose of MK-3402 on 2 separate occasions. In Period 1, participants will receive a single IV dose of MK-3402 immediately following completion of their normally scheduled HD, followed by 48-hours plasma and 24-hours urine sampling, where possible, for PK assessment of MK-3402.

In Period 2, participants will receive a single IV dose of MK-3402 approximately 30 minutes prior to their normally scheduled HD followed by 48-hours plasma and 12-hours urine sampling, where possible, for PK assessment of MK-3402. During this dialysis session, additional plasma and dialysate samples will be taken for MK-3402 analysis.

There will be a washout period of at least 6 days between MK-3402 dosing in Periods 1 and 2 of Panel E.

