### **8.10.2 Treatment Period**

Following confirmation that each participant meets inclusion/exclusion criteria and that all predose procedures have been completed, participants will be assigned a unique allocation number associated with a specific treatment sequence as defined by a computer allocation schedule.

Before each treatment, participants will report to the CRU on Day -1 or at a time specified by the investigator. Participants will fast from all food and drink except for water, for at least 8 hours before study drug administration and at least 1 hour after study drug administration (refer to Section 5.3.1 for specific dietary restrictions during dosing).

Participants will remain in the CRU up to 24 hours postdose. Participants may be required to remain in the CRU for longer than 24-hours postdose at the discretion of the investigator.

Participants in Panels A to D will be administered the assigned treatment in the morning. The exact clock time of dosing should be recorded.

ESRD participants on HD (Panel E) will receive HD as per their regular schedule and blood and dialysate sampling be collected as outlined in the SoA (Section 1.3).

Dosing in Period 1 will occur immediately following completion of a normally scheduled HD session. Panel E will have a washout period of at least 6 days between the dosing of study drug in each treatment period. Dosing in Period 2 will occur approximately 30 minutes prior to the normally scheduled HD session. The subsequent HD session should initiate immediately following the 30-minute blood draw, VS and ECG.

In Period 2, the HD period will be approximately 4 hours for all participants. Blood samples collected during HD will be collected from both the pre-dialyzer and post-dialyzer blood lines.

The blood flow, dialysate flow, and the make and model of the dialyzer will be recorded.

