### 9.4 Analysis Endpoints

The primary PK endpoints are plasma MK-3402 AUC0-inf, Ce0, Tmax, elimination terminal t1/2, CL, and Vd following a single MK-3402 IV dose in participants with mild, moderate, severe renal impairment, ESRD or in healthy matched control participants.

The secondary PK endpoints are plasma MK-3402 CLD,plasma or the dialysate CD, AED, AED (%dose), and CLD,dialysis and urine MK-3402 Ae0-24, Fe, and CLr following a single MK-3402 IV dose in participants with mild, moderate, severe impairments, ESRD or in healthy matched control participants.

The secondary safety endpoints are AEs, VS, 12-lead ECGs, and laboratory safety tests.

The exploratory endpoint is eGFR at baseline.

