## 9.6 Statistical Methods

### Pharmacokinetics:

#### **Primary Analysis**

If a different group of healthy matched control participants is needed to match the mean age and BMI for the RI and ESRD groups, then separate analyses will be performed for the populations as follows:

- Mild RI and moderate RI versus an appropriate group of healthy matched control participants;
- Severe RI versus an appropriate group of healthy matched control participants;
- ESRD participants (non-HD and HD) versus an appropriate group of healthy matched control participants.

If a single set of healthy matched control participants can be used for comparison with all RI and ESRD groups, the following analysis pooled over all populations will be used.

Separately for each pharmacokinetic parameter, individual values of plasma MK-3402 AUC0-inf and Ce0i will be natural log-transformed and evaluated with a linear fixed-effects model containing a categorical effect for populations. The REPEATED statement with the GROUP=Population option will be used in SAS PROC MIXED to estimate separate variances for each population. The Kenward and Roger adjustment will be used to calculate the denominator degrees of freedom for the fixed-effect (DDFM=KR).

Ninety-five percent (95%) CIs for the least squares means for each population will be constructed on the natural log scale and will reference the t-distribution. Exponentiating the least-squares means and their corresponding 95% CIs will yield estimates for the population GMs and CIs about the GMs on the original scale.

To compare participants with RI in each of the renal categories (mild RI, moderate RI, severe RI, ESRD non-HD and ESRD HD) to matching participants with normal renal function, a 2-sided 90% CI for the true difference in means (RI - normal renal function) will be calculated for each PK parameters (AUC0-inf and Ce0i) using the mean square error from the model and referencing a t-distribution. For each of the RI populations, these confidence limits will be exponentiated to obtain the 90% CI for the true GMRs (RI/normal renal function) for each PK parameter.

Figures showing individual PK values with GMs (95% CIs) by population, plotted on the natural log scale, will be provided for AUC0-inf and Ceoi.

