Summary Statistics using BSA un-normalized eGFR: The participants will be recategorized into different renal categories based on their BSA un-normalized eGFR and nonmodel based summary statistics by population will be provided for (plasma AUC0-inf, Ceoi, Tmax, elimination terminal t1/2, CL, and Vd, and urine Ae0-24, Fe, and CLr, as applicable).

Analysis using CrCl (CG equation): The participants will be recategorized into different renal categories based on their CrCl obtained from CG equation and nonmodel based summary statistics by population will be provided for (plasma AUC0-inf, Ceoi, Tmax, elimination terminal t1/2, CL, and Vd, and urine Ae0-24, Fe, and CLr, as applicable).

Individual values will be listed for each PK parameter (plasma MK-3402 AUC0-inf, Ceoi, Tmax, elimination terminal t1/2, CL, and Vd, plasma MK-3402 CLD,plasma or the dialysate CD, AED, AED (%dose), and CLD,dialysis, and urine MK-3402 Ae0-24, Fe, and CLr) by population, and the following (nonmodel-based) descriptive statistics will be provided: N

(number of subjects with nonmissing data), arithmetic mean, standard deviation, arithmetic percent CV (calculated as 100 x standard deviation/ arithmetic mean), median, minimum, maximum, geometric mean, and geometric percent CV (calculated as 100 x sqrt( exp(s) - 1), where s is the observed variance on the natural log-scale).

**Safety:** The safety and tolerability of MK-3402 will be monitored by clinical assessment of adverse experiences and other safety measurements (eg, labs, VS, ECGs).

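### Volume of distribution in the ESRD dialysis period (Panel E, Period 2) will be inflated, because a dialysis session of about 4 hours lies inside the profile from which it is calculated

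*Combined protocol and SAP*

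**What the plan says.** The primary objective in Section 3 compares plasma parameters, with CL, Vd and terminal t1/2 among the examples, in participants with "varying degrees of renal impairment (mild, moderate, severe, ESRD before HD, ESRD after HD) to those of healthy matched control participants". Section 9.4 lists as primary endpoints AUC0-inf, Ceoi, Tmax and "elimination terminal t 1/2 , CL, and V d following a single MK-3402 IV dose in participants with mild, moderate, severe renal impairment, ESRD"; the same sentence also covers the controls.

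Section 9.6 names both ESRD conditions as populations, comparing participants "in each of the renal categories (mild RI, moderate RI, severe RI, ESRD non-HD and ESRD HD) to matching participants with normal renal function". Only two parameters are modelled: "individual values of plasma MK-3402 AUC0-inf and Ce0i will be natural log-transformed and evaluated with a linear fixed-effects model". The rest are listed and summarised descriptively by population: "Individual values will be listed for each PK parameter (plasma MK-3402 AUC0-inf, Ceoi, Tmax, elimination terminal t1/2, CL, and Vd", followed by the dialysis and urine parameters.

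In Period 1 the dose is given just after a dialysis session. In Period 2 it is given "approximately 30 minutes prior to their normally scheduled HD followed by 48-hours plasma and 12-hours urine sampling" (Section 4.1). The Period 2 schedule (Section 1.3.3) states: "HD session will be initiated immediately following the 0.5-hr postdose blood draw, VS and ECG". Section 8.10.2 adds: "In Period 2, the HD period will be approximately 4 hours for all participants".

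Nowhere do the documents give a formula for CL or Vd, a sampling window for the terminal slope, or a rule that omits, corrects or labels any Period 2 value.

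**The concern.** A volume obtained from clearance and terminal half-life is meaningful only if one clearance applies throughout the profile. In Period 2 it does not. Dose/AUC0-inf averages over a stretch with dialysis and a longer stretch without, whereas a terminal slope fitted after the session reflects only the second. Combining the two gives a volume that is too large even when distribution is unchanged.

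At stake is a spurious value for a primary endpoint. Section 4.3 builds its projections on Vd staying constant as renal function falls. A Period 2 Vd well above the healthy value would seem to contradict that assumption, and in the same participants would disagree with Period 1, purely because of how it was computed.

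**Working it through.** **Inputs.** From the projection table in Section 4.3 (100 mg): healthy CL 4.18 L/h, AUC0-inf 50.9 µM·h, t1/2 4.47 h; ESRD not on dialysis CL 2.17 L/h, AUC0-inf 98.0 µM·h, t1/2 8.61 h. From Table 3: CL, t1/2 and Vd at eight dose levels. From Sections 1.3.3 and 8.10.2: dialysis from about 0.5 to 4.5 h. The fraction removed, f, is an assumption. Section 4.3.1 says the extent of removal is unknown for MK-3402 and mentions about 50% for a similar compound, so 10% to 60% is shown.

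**Step 1: which Vd does the programme use?** Test Vd = CL × t1/2 / ln 2 on Table 3. At 100 mg, 4.18 × 4.47 / 0.693 = 27.0 L, as printed. The eight doses from 25 to 1100 mg give 21.8, 27.8, 27.0, 23.3, 25.2, 24.2, 23.0 and 21.5 L. The printed values are 21.8, 27.8, 27.0, 23.3, 25.2, 24.3, 22.9 and 21.5 L, so all agree within 0.1 L. The five projection rows in Section 4.3 give 26.94 to 26.96 L, and their AUC values reproduce to 0.1.

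**Step 2: what dialysis does to the formula.** Let CL be the participant's own clearance. By mass balance with linear kinetics, Dose = CL × AUC0-inf + f × Dose. Hence:

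- AUC0-inf (Period 2) = (1−f) × Dose / CL
- Dose / AUC0-inf (Period 2) = CL / (1−f)
- the terminal slope after dialysis ends is unchanged, so Vd (Period 2) = Vd / (1−f)

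**Step 3: numbers.** The off-dialysis ESRD Vd is 2.17 × 8.61 / 0.693 = 26.95 L. At f = 50%, AUC0-inf is 0.5 × 98.0 = 49.0 µM·h, CL is 2.17 / 0.5 = 4.34 L/h, and Vd is 26.95 / 0.5 = 53.9 L. A one-compartment simulation with a 30-minute infusion and extra clearance from 0.5 to 4.5 h agrees at every f:

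| f | Dose/AUC0-inf (L/h) | Terminal t1/2 (h) | Vd (L) | Vd inflation |
|---|---|---|---|---|
| 0 (Period 1) | 2.17 | 8.61 | 26.95 | 1.00 |
| 10% | 2.41 | 8.61 | 29.9 | 1.11 |
| 30% | 3.10 | 8.61 | 38.5 | 1.43 |
| 40% | 3.62 | 8.61 | 44.9 | 1.67 |
| 50% | 4.34 | 8.61 | 53.9 | 2.00 |
| 60% | 5.43 | 8.61 | 67.4 | 2.50 |

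**Step 4: does the result depend on the model or the volume formula?** P001 reports a biphasic decline, so a two-compartment model was calibrated to the healthy 100 mg Ceoi (14.8 µmol/L), CL and t1/2, with Vss 20.7 L (Table 5 gives 20.6 and 20.8 L). At f = 50%, CL × t1/2 / ln 2 goes from 23.5 to 47.1 L, again 2.00-fold, with terminal t1/2 7.52 h in both cases. The absolute litres depend on the model; the ratio does not. A moment-based Vss is also inflated: 34.7 against 20.7 L, or 34.7 / 20.7 = 1.68-fold.

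**Step 5: scale.** The projected true Vd ratio of ESRD to healthy is 26.95 / 26.96 = 1.00. The geometric CV of Vd in healthy participants at 100 mg is 7.5% (Table 3).

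**The case against.** The strongest reply is that little depends on this. The primary estimation names AUC0-inf alone, only AUC0-inf and Ceoi are modelled, and no ratio, confidence interval or sample-size figure uses Vd. That stands, and it limits the importance of the point.

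It can also be said that the Vd formula is inferred from another study, that the Section 3 parameter list gives examples only, and that the Section 9.6 list is generic, since it includes dialysate parameters that exist only for Period 2. So the plan never says outright that Vd will be computed for Period 2. That is fair, but Sections 3, 9.4 and 9.6 together lead there, nothing excludes it, and the moment-based alternative is inflated too.

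A reader might infer more than the documents support:

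- *That Period 2 CL is equally an artefact.* It is not. Dose/AUC0-inf is a valid average total clearance over a profile that includes dialysis and, at a fixed dose, is proportional to the reciprocal of the AUC0-inf already compared in the primary analysis. Nor does it mimic a disease effect: it moves towards the healthy value, reaching 4.18 L/h at f = 1 − 2.17/4.18 = 48%. The risk is that, unlabelled, it is read as the participant's own clearance.
- *That terminal t1/2 is wrong because it shows no dialysis effect.* Fitted after dialysis ends, it is a correct off-dialysis value and should agree with Period 1. The gap is that the plan states no fitting window.
- *That the effect of dialysis goes unassessed.* Section 9.4 has dedicated dialysis-clearance and dialysate endpoints, and the secondary analysis in Section 9.6 compares AUC0-inf and Ceoi between the two periods within participants.

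**Conclusion.** The point holds for Vd. If the plan is followed with the programme's usual formula, Period 2 Vd is too large by 1/(1−f): 1.1-fold at 10% removal, 2.0-fold at 50% and 2.5-fold at 60%. A moment-based Vss would be about 1.7-fold too large at 50%. At the higher fractions the error is far outside the spread seen in healthy participants.

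This rests on linear kinetics, a terminal slope fitted after dialysis ends, and an assumed f, because removal of MK-3402 is unknown and the 50% figure belongs to another compound. Period 2 CL and t1/2 need labels, not removal. The modelled AUC0-inf and Ceoi results and the stated precision are unaffected. The consequence is one misleading descriptive value for a primary endpoint, worth correcting before the analysis is run.

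**What to change.** In Sections 3, 9.4 and 9.6:

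- Take ESRD Vd from Period 1 only, and omit Vd for Period 2.
- Label Period 2 CL as total clearance including one HD session, and use Period 1 for off-dialysis CL.
- Give the formulas for CL and Vd. State that the Period 2 terminal slope uses only samples taken after dialysis ends, and label the result off-dialysis t1/2.
- Optionally, add an on-dialysis half-life from the pre-dialyzer plasma samples already scheduled during the session.

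The cost is wording in the objectives and analysis sections, with no new samples, visits or models. The one loss is that Vd is no longer reported for Period 2; the same six participants supply it in Period 1.

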## 9.7 Interim Analyses

Not applicable.

## 9.8 Multiplicity

There is no prespecified hypothesis; therefore, no multiplicity adjustment is needed.

## 9.9 Sample Size and Power Calculations

The sample size selected for each population to evaluate the effect of RI on the PK of MK-3402 was not chosen to satisfy any a priori statistical requirement. This sample size (n= 6 participants per panel) has historically been shown to be sufficient for studies of this type and should provide adequate data to support the planned analyses. Nevertheless, estimates of the expected precision of the estimates, based on these sample sizes are presented below.

The precision of the estimated ratios of geometric means (renal impairment / normal renal function) of PK parameters obtained from this study can be assessed by calculating the half-width of the 90% CIs expected for the given sample size and assumed variability. The pooled between-subject standard deviation (on the natural log scale) for MK-3402 AUC0-inf after administration of 25 to 1100 mg MK-3402 observed in P001 is 0.112 ln(μM•hr). Assuming a sample size of 6 participants per population and observed between-subject SDs as given above, then the half width of the 90% CIs of GMRs for MK-3402 AUC0-inf on the log scale will be 0.11. The lower and upper 90% confidence limits for the true GMRs will be given by OBS/1.12 and OBS\*1.12 for AUC0-inf, where OBS is the observed GMR. Thus, for example, if the observed GMR for AUC0-inf was 1.50, then the 90% CI for the GMR would be 1.33 to 1.68.

## 10 SUPPORTING DOCUMENTATION AND OPERATIONAL CONSIDERATIONS

### 10.1 Appendix 1: Regulatory, Ethical, and Study Oversight Considerations

#### 10.1.1 Code of Conduct for Clinical Trials

Merck Sharp and Dohme Corp., a subsidiary of Merck & Co., Inc. (MSD)

#### Code of Conduct for Interventional Clinical Trials

##### I. Introduction

###### A. Purpose

MSD, through its subsidiaries, conducts clinical trials worldwide to evaluate the safety and effectiveness of our products. As such, we are committed to designing, implementing, conducting, analyzing, and reporting these trials in compliance with the highest ethical and scientific standards. Protection of participants in clinical trials is the overriding concern in the design and conduct of clinical trials. In all cases, MSD clinical trials will be conducted in compliance with local and/or national regulations (including all applicable data protection laws and regulations), and International Council for Harmonisation Good Clinical Practice (ICH-GCP), and also in accordance with the ethical principles that have their origin in the Declaration of Helsinki.

